## 5.2 Microbiological Methods

### 5.2.1 Microbial Sample Collection / Scrub Cup Technique

Quantitative cultures (screening baselines, treatment day baselines and post treatment samples) will be obtained by a modification of the cylinder sampling technique of Williamson-Kligman scrub cup technique following ASTM E1874-14 "Standard Test Method for Recovery of Microorganisms from Skin using the Cup Scrub Technique". To collect the samples, a sterile scrub cup (2.20 cm I.D.) will be placed on the site and held firmly to the skin. 3.0 ml of SSF++ will be pipetted into the cup and the skin will be scrubbed in a circular motion with moderate pressure for 1 minute using a sterile rubber policeman. Using a sterile transfer pipette, the SSF++ will be removed and placed in a sterile test tube. An additional 3.0 ml of fresh SSF++ will be pipetted into the cup and the scrub procedure will be repeated. This solution will be pooled with the first solution collected.

### 5.2.2 Bacterial Enumeration Methods

Following sample collection, vortex the sample for 15 seconds and 10-fold serial dilutions will be prepared using PBW. One ml aliquots of appropriate dilutions will be pour-plated in TSA+N. Samples must be plated within 30 minutes of collection.

Serial dilutions of collected baseline screening samples as follows:

- for groin sites: 1 serial dilution ( $10^{-3}$ )
- for abdomen sites: 1 serial dilution ( $10^{-1}$ )

Serial dilutions of collected treatment day (D0) samples as follows:

for groin sites:

- Baseline: 3 serial dilutions ( $10^{-3}$ ,  $10^{-4}$  and  $10^{-5}$ )
- 30 seconds: 4 serial dilutions ( $10^0$ ,  $10^{-1}$ ,  $10^{-2}$  and  $10^{-3}$ )
- 10 minutes: 4 serial dilutions ( $10^0$ ,  $10^{-1}$ ,  $10^{-2}$  and  $10^{-3}$ )
- 6 hours: 4 serial dilutions ( $10^0$ ,  $10^{-1}$ ,  $10^{-2}$  and  $10^{-3}$ )

for abdomen sites:

- Baseline: 3 serial dilutions ( $10^{-1}$ ,  $10^{-2}$  and  $10^{-3}$ )
- 30 seconds: 3 serial dilutions ( $10^0$ ,  $10^{-1}$  and  $10^{-2}$ )
- 10 minutes: 3 serial dilutions ( $10^0$ ,  $10^{-1}$  and  $10^{-2}$ )
- 6 hours: 3 serial dilutions ( $10^0$ ,  $10^{-1}$  and  $10^{-2}$ )

After  $72 \pm 4$  hours of aerobic incubation at  $30 \pm 2^\circ\text{C}$ , colonies will be manually counted and viable cells in the original sample will be calculated according to SOPs. After incubation, plates may be refrigerated up to 48 hours prior to counting.

Bacterial colonies enumerated manually within the countable range 25-250 from each dilution will be recorded on the appropriate CRFs for each subject. The average number of microorganisms recovered (CFU/cm^2) from the skin during screening and treatment day will be calculated using the formula to convert the volume of sample collected into  $\log_{10}\text{CFU}/\text{cm}^2$  of skin:

$$R = \log_{10} \left[ \frac{F \left( \frac{\sum_{i=1}^3 c_i}{n} \right) D}{A} \right]$$

Where:

$R$  = the average colony-forming unit count in  $\log_{10}$  scale per  $\text{cm}^2$  of sampling surface

$F$  = total number of ml of stripping fluid added to the sampling cylinder; in this study,  $F = 6$  ml

$\frac{\sum_{i=1}^3 c_i}{n}$  = average of the triplicate colony counts used for each sample collected

$D$  = dilution factor of the plate counts

$A$  = inside area of the cylinder in  $\text{cm}^2$ ; in this study,  $A = 3.80 \text{ cm}^2$  for the 2.2-cm diameter cylinder.

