## 2 Study Objectives

### 2.1 Efficacy objectives

The objective of this study is to demonstrate immediate (30 seconds and 10 minutes) and persistent (6 hours) antimicrobial efficacy for patient preoperative skin preparation of product A and product B compared with product C.

To demonstrate the immediate antimicrobial efficacy at 30 seconds and 10 minutes post-application the following criteria should be met on both body area (abdomen and groin):

- non-inferiority of the ATE of the product A and product B compared to product C (the upper two-sided 95% confidence bound of the post-application microbial counts corrected for Baseline of the A-C or B-C should be less than  $0.5 \log_{10}$ ).

To demonstrate the persistent efficacy for patient preoperative skin preparation, the microbial counts ( $\log_{10}$  CFU/cm^2) at 6 hours post-application should be lower than or equal to the baseline for 100 percent of the subjects in each body area.

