### **3.6.2 Subject Discontinuation and Withdrawal**

The PI may discontinue individual subjects from the study at any time. Subjects may voluntarily withdraw from the study at any time without reason or consequence. A reason will be reported, if provided. The PI will provide a written report on the appropriate CRF including the date and reason for discontinuance. Subjects who qualify on Screening Day and begin the treatment phase may not be re-entered into the study, regardless of whether or not they completed the study.

Additional subjects will be recruited and screened, as necessary, to meet the required number of evaluable treatment sites per body area, per treatment, per collection time.

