## 4 Study Population

The trial will utilize ER's subject database and would not require the recruitment of subjects through study-specific advertisement.

Subjects must satisfy all Screening Day and Treatment Day Inclusion/Exclusion Criteria prior to screening sample collection and Treatment Day procedures.

Screening Day Baseline microbial count requirements are at least  $3.11 \log_{10}$  CFU/cm^2 bilaterally on the abdomen, and at least  $5.00 \log_{10}$  CFU/cm^2 bilaterally on the groin except for subjects enrolled for Neutralization study.

Treatment Day Baseline microbial count requirements are in the range of  $3.11$  to  $5.50 \log_{10}$  CFU/cm^2, inclusive, on the abdomen, and  $5.00$  to  $7.50 \log_{10}$  CFU/cm^2, inclusive, on the groin except for subjects enrolled for Neutralization study.

Subjects must qualify on both body area (abdomen and/or groin) to be admitted into testing, except for Neutralization study.

Both the right and left sides of the abdomen and groin must meet the minimum Screening Day values stated in the Inclusion Criteria to qualify, except for Neutralization study and except when one anatomical area (abdomen or groin) has completed the valid cases for all the products, then additional subjects will be screened only for the leftover area.

Additional subjects will be recruited and screened, as necessary, to meet the required number of evaluable treatment sites per body area, per collection time.

All subjects will be given verbal and written information about the study procedures - Subject Instructions for Main Study ([Appendix 17.5.1](#)) will be provided to each subject for the Washout phase of the study and Subject Instructions for Neutralization ([Appendix 17.5.2](#)) will be provided to each subject for the Neutralization Study.

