## 9 Statistics

### 9.1 Data sets analyzed

Subjects with treatment day baseline bacterial count in the range of 3.11 to 5.50  $\log_{10}/\text{cm}^2$ , inclusive, on the abdomen and 5.00 to 7.50  $\log_{10}/\text{cm}^2$ , inclusive, on the groin will be included in the analysis.

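### 6-hour samples are not plated far enough to count a persistence failure when baseline exceeds 4.60 (abdomen) or 5.60 (groin) log10 CFU/cm2, and the protocol prints no score for an overgrown last plate

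*Combined protocol and SAP*

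**What the plan says.** Section 5.2.2 sets the plating. On the abdomen the plan is "6 hours: 3 serial dilutions", ending at 10^-2. On the groin it is "6 hours: 4 serial dilutions", ending at 10^-3. Treatment-day baselines go further, to 10^-3 on the abdomen and 10^-5 on the groin. For reading the plates, the section says "Bacterial colonies enumerated manually within the countable range 25-250 from each dilution will be recorded on the appropriate CRFs for each subject". It prints no value, flag or substitution for a sample with more than 250 colonies on its last plate. Beyond the printed formula, "viable cells in the original sample will be calculated according to SOPs"; those SOPs are not part of the document.

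Section 9.1 admits "Subjects with treatment day baseline bacterial count in the range of 3.11 to 5.50" log10 on the abdomen, and 5.00 to 7.50 on the groin. Section 9.3.1 scores each site a success at 6 hours if its count is no higher than its baseline, and summarises the rates descriptively. Section 2.1 sets the bar: the 6-hour count "should be lower than or equal to the baseline for 100 percent of the subjects in each body area". Section 9.5 does not impute missing counts and requires them to be described in the study report. Its examples are laboratory error and loss to follow-up; it does not say whether an overgrown plate is missing.

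**The concern.** Persistence compares two counts from the same site, but the two are measured over different ranges. Baseline can be read across the whole qualifying window. The 6-hour count cannot: its upper limit lies inside that window.

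Most results are still clear. A countable 6-hour plate under a baseline above the ceiling is a certain success. An overgrown last plate with a baseline at or below the ceiling is a certain failure. What remains is an overgrown last plate with a baseline above the ceiling. For example, with a groin baseline of 7.0, 6-hour counts of 5.8 (success) and 7.2 (failure) both exceed 250 colonies on the 10^-3 plate. At such baselines only successes can be counted within 25-250.

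Because the criterion is 100 percent, a single site can decide it. The result could then depend on a laboratory convention that the protocol does not print.

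**Working it through.** **Inputs.** F = 6 ml, A = 3.80 cm2, 1 ml plated, triplicate counts, range 25-250 and the dilutions (section 5.2.2); baseline windows (9.1); success definition (9.3.1); 75 subjects and 50 sites per product per body area (9.2).

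**Plan's own figures.** 75 subjects × 2 sides / 3 products = 50 sites per product, as stated. Cup area = π × 1.10^2 = 3.80 cm2, as stated.

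**Ceilings.** R = log10(F × c × D / A), with c = 250 and D from the last plate:

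| Sample | Calculation | Ceiling | Top of baseline window |
|---|---|---|---|
| Abdomen, 6 h | log10(6 × 250 × 10^2 / 3.80) | 4.596 | 5.50 |
| Groin, 6 h | log10(6 × 250 × 10^3 / 3.80) | 5.596 | 7.50 |
| Abdomen, baseline | log10(6 × 250 × 10^3 / 3.80) | 5.596 | 5.50 |
| Groin, baseline | log10(6 × 250 × 10^5 / 3.80) | 7.596 | 7.50 |

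**Affected part of the window.** Abdomen: (5.50 − 4.596) / (5.50 − 3.11) = 0.904 / 2.39 = 38%. Groin: (7.50 − 5.596) / (7.50 − 5.00) = 1.904 / 2.50 = 76%.

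**Second condition.** The 6-hour reduction must be smaller than baseline minus ceiling: below 0.90 (abdomen) or 1.90 (groin) at the highest permitted baseline, and below 0.45 or 0.95 in the middle of the affected zone.

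**Example, groin baseline 7.0.** Colonies on the 10^-3 plate: 10^5.8 × 3.80 / 6 / 1000 = 400, and 10^7.2 × 3.80 / 6 / 1000 = 10,038. Both are over 250. On a 10^-5 plate the second would read 100.

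**One true failure of this kind among 50 sites.** Capped at the ceiling: 50/50, because baseline is above the ceiling. Treated as missing: 49/49. Scored as a failure: 49/50 = 98%.

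**How many samples (illustration only).** The documents give neither the baseline distribution nor the 6-hour reduction. Assume baseline uniform over the window and reduction normal with mean m and SD 1.0. Undetermined sites per 50 = (50 / window) × ∫ Φ(b − ceiling − m) db, from the ceiling to the top of the window. The share that are true failures is (affected fraction × Φ(−m)) divided by the undetermined fraction.

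| Mean reduction m | Abdomen: sites per 50 | of which true successes | Groin: sites per 50 | of which true successes |
|---|---|---|---|---|
| 2 | 1.3 | 66% | 6.9 | 87% |
| 3 | 0.13 | 80% | 1.4 | 96% |
| 4 | 0.006 | 89% | 0.13 | 99% |

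If baselines instead thin out upward (half-normal from the window floor, SD 0.75, truncated at the top), the sites per 50 fall to 0.10, 0.009 and below 0.001 (abdomen) and 1.5, 0.18 and 0.01 (groin). True successes are then 48% to 76% of them on the abdomen and 67% to 93% on the groin.

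**Cost of counting every undetermined sample as a failure (groin, uniform baseline, m = 3, 50 independent sites).** True failure probability per site is Φ(−3) = 0.00135, so the true chance of 100 percent is (1 − 0.00135)^50 = 93%. With undetermined samples counted as failures the probability is 1.375/50 + 0.239 × 0.00135 = 0.0278, and the chance is (1 − 0.0278)^50 = 24%.

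**The case against.** The best case against the point is that it will seldom arise and may already be covered. An antiseptic that lowers counts by 3 or 4 log10 at 6 hours leaves few overgrown plates. Appendix 17.7.1 puts normal skin flora at about 10^2 to 10^5 CFU/cm2, so baselines near 7.50 may be uncommon even after screening for high counts. Handling of over-range plates is also a natural subject for the cited SOPs. All of this stands, and it limits the size of the point. It does not remove it: a persistence test exists to detect a return above baseline, and that is the event the stated plating cannot count at high baselines.

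Two stronger readings are tempting.

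- **Silent loss.** A reader might infer that a failing site would simply disappear. Section 9.5 requires missing data to be described in the report, so the documents do not support that.
- **Replacement.** A reader might infer that the site would be replaced, because section 3.6.2 recruits "to meet the required number of evaluable treatment sites per body area, per treatment, per collection time" and section 4 has similar wording. But sections 9.1 and 9.2 define inclusion and the target by baseline count, which such a site meets, and nowhere is an overgrown plate called non-evaluable. The inference rests on the mention of collection time alone.

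**Conclusion.** The point holds as a flaw in the stated plating. Under the dilutions and countable range in 5.2.2, a 6-hour count above baseline cannot be measured when baseline exceeds 4.60 (abdomen) or 5.60 (groin) log10 CFU/cm2, and the protocol does not say how the resulting overgrown plate is scored. This follows from the plan's own formula and needs no outside assumption. That no rule exists at all is not established, since the SOPs were not available.

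Its practical size is uncertain and probably small. The 38% and 76% must not be read as shares of sites or of failures: they are widths of the baseline window, and a small 6-hour reduction is needed as well. Nor can the documents support a figure for how much the chance of meeting the criterion is inflated, because they give no failure rate. Most undetermined samples would be true successes in nearly all the settings tried. What makes the gap worth closing is the 100 percent rule, under which one capped or omitted true failure changes the conclusion. The change is recommended; the gap does not invalidate the persistence objective.

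**What to change.** In 5.2.2, plate 6-hour samples to the same top dilution as baseline: 10^-3 on the abdomen and 10^-5 on the groin. State that a 6-hour sample with more than 250 colonies at its highest dilution is scored a persistence failure. With ceilings of 5.60 and 7.60, every qualifying baseline lies below the ceiling, so that score is always correct.

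Cost, in triplicate for 75 subjects (150 sites per body area): current treatment-day plates are 12 × 3 × 150 = 5,400 (abdomen) and 15 × 3 × 150 = 6,750 (groin), together 12,150. The change adds 1 × 3 × 150 = 450 and 2 × 3 × 150 = 900, together 1,350, or 11%. It needs no new visits or skin samples.

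If plating is not changed, put a rule in 9.3.1. An overgrown 6-hour sample is a failure when baseline is at or below the ceiling. Otherwise report it as undetermined, keep it in the denominator, and show the 100 percent criterion both ways, with these samples counted as successes and as failures. Note beside the second display that it is conservative, since most such samples would probably be true successes. This costs only wording, but it shows the ambiguity without resolving it.

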### 5.2.3 Neutralization Validation

A Neutralization study will be conducted to demonstrate that the neutralizers used in the sampling solution and media are effective in inhibiting the antimicrobial properties of the test products without impairing the recovery of challenge microorganisms. *Staphylococcus epidermidis*, ATCC 12228 (MSSE), *Staphylococcus epidermidis*, ATCC 51625 (MRSE) will be used as challenge microorganisms.

Neutralization procedures will follow guidelines provided by ASTM E1054-08 (reapproved 2013), "Standard Test Methods for Evaluation of Inactivators of Antimicrobial Agents". The full procedure is attached as [Appendix 17.7](#).

## 6 Assessment of Efficacy

### 6.1 Efficacy Parameters

The measure of antimicrobial efficacy will be the  $\log_{10}$  CFU/cm^2 of skin flora at the abdominal and groin sites 30 seconds, 10 minutes and 6 hours following study products application relative to the Treatment Day baseline  $\log_{10}$  counts.

### 6.2 Assessment Methods

Efficacy will be assessed by sampling the skin using the cup scrub method and analysis methods described in [Section 5.2](#).

## 7 Risk / Benefit Assessment

### 7.1 Potential Risks

Subjects participating in this study could experience side effects to the skin such as:

- Redness
- Swelling
- Burning, stinging and itching
- Cracking
- Peeling
- Small blisters or sores (in uncommon cases)
- Rash or other allergic reaction including in rare cases anaphylaxis
- Irritation
- Pain
- Localized rash or inflammation (dermatitis)
- Impetiginized eczema (infected eczema or infected dry skin and recurring skin rashes)
- Application site hypopigmentation (lightening of skin) or hyperpigmentation (darkening of skin).

Subjects may also experience folliculitis from clipping.

There may be risks from participating in this study that are unknown.

### 7.2 Potential Benefits

There are no direct benefits to the subject for participation in this study.

## 8 Assessment of Safety

### 8.1 Safety Parameters

The principal measures of safety will be skin irritation scores and the incidence of adverse events reported during the study.

Adverse events will be captured from the time screening baseline samples are taken to the time of subject discharge from the study. Adverse events will be categorized in relationship to the product that was applied to the specific skin site. All local and systemic adverse events observed or reported to the investigator will be evaluated.

The severity, duration, causal relationship to the study product and study procedure, action taken (study related and subject related), study impact, outcome of the event; will be described for all adverse events.

## 8.2 Assessment Methods for Skin Irritation

All randomized subjects will be considered evaluable for safety. Skin irritation scores based on the scale from [Appendix 17.8](#) will be reported for any subject who is scored with a 1 or more at any observation [baseline (screening day and treatment day), clipping/re-clipping (prior to screening day, treatment day or neutralization day), prior/post-application to 30 seconds, 10 minutes, and 6 hours sampling procedures], in any category for any site.

Adverse events (including post treatment skin irritation scores of 3), will also be summarized. Summary tables will present incidence rates of adverse events by treatment group for all subjects who enter the treatment period. Listings of adverse events will be provided.

A corresponding rating score for each individual skin condition, for each site will be recorded in the subject's CRF. (See [Appendix 17.8](#), which includes the following four independent evaluation categories: Erythema, Edema, Rash, and Dryness).

If an irritation score of 1 or greater for any individual skin condition prior to the baseline sample collection (at either the screening or treatment day phases) is assigned, the subject will be excluded from the study (no study treatment will be applied).

If an irritation score of 3 for any individual skin condition at any observation period is assigned, the subject will be discontinued from the study and an adverse event will be recorded. See [Section 8.3](#) (Adverse Events).

## 8.3 Adverse Events

The PI is responsible for identifying adverse events that occur to each subject throughout the study and follow-up period. An adverse event can occur at any time during the conduct of the study, in any phase of the study or after the study is completed. An adverse event can be identified by the PI or reported by the subject.

Definitions:

### Adverse Event/Experience

An Adverse Event/Experience is any unexpected or undesirable experience occurring to a subject during a study, which may or may not be related to the test product.

All adverse events, regardless of severity or the causal/effect relationship, will be recorded. The severity of the effect will be noted as *Mild*, *Moderate*, or *Severe* according the following definitions:

Mild Awareness of signs or symptom, but easily tolerated.

Moderate Discomfort to a degree as to cause interference with normal daily life activities and /or requiring medication.

Severe Incapacity with inability to work or do usual daily life activities and requiring medical attention/intervention.

### Causal Relations of Adverse Event/Experience

When determining the causal/effect relationship to the test product, the relationship will be described as *Not related*, *Unlikely related*, *Possibly related* or *Related*.

The following definitions will be utilized:

Not related	No association to the test product. Related to other etiologies such as concomitant medications or conditions or subject's known clinical state.
Unlikely related	Uncertain association. Other etiologies are also possible.
Possibly related	Clear-cut association with improvement upon withdrawal of the test product. Not reasonably explained by the subject's known clinical state.
Related	An adverse event with a clear-cut temporal association with exposure to study materials and cannot reasonably be explained by the subject's known clinical state. Association with study material is confirmed by laboratory testing if possible.

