#### Recording and Reporting

The PI or designee records all adverse events on an Adverse Event Form in the subject's CRF.

The PI must promptly report all treatment related adverse events to the PDI study monitor.

All SAE must be reported to the:

- Sponsor within 24 hours of the PI awareness/notification of the event.
- IRB/IEC within 10 working days of the PI awareness/notification of the event.

If a subject has no adverse event during the study, the absence of such must be recorded on the CRF.

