### 9.4 Safety Analysis

All treated subjects will be considered evaluable for safety. Skin irritation scores will be reported for any subject who is scored with a 1 or more at any observation (baseline screening day, baseline treatment day, post-application/prior to 30 seconds, 10 minutes, and 6 hours sampling procedures), in any category for any site.

Adverse events (including post treatment skin irritation scores of 3), will also be summarized. Summary tables will present incidence rates of adverse events by treatment group for all subjects who enter the treatment period. Listings of adverse events will be provided.

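### Section 8.3 allows an uncertain association to be coded only as *Unlikely related*, and prompt reporting depends on an undefined term, *treatment related*

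*Combined protocol and SAP*

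**What the plan says.** Section 8.3, under Causal Relations of Adverse Event/Experience, sets four categories and says that these definitions are to be used.

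- *Not related*: no association with the product; the event is put down to other causes.
- *Unlikely related*: "Uncertain association. Other etiologies are also possible".
- *Possibly related*: "Clear-cut association with improvement upon withdrawal of the test product", together with "Not reasonably explained by the subject's known clinical state".
- *Related*: "An adverse event with a clear-cut temporal association with exposure to study materials", which the subject's known clinical state cannot reasonably explain, with laboratory confirmation where possible.

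Under Recording and Reporting, the same section states: "The PI must promptly report all treatment related adverse events to the PDI study monitor". It does not say which of the four categories count as treatment related. Serious events follow a separate rule with no causality condition. They go to the "Sponsor within 24 hours of the PI awareness/notification of the event", and to the ethics bodies within 10 working days.

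Two further rules limit what the categories can affect. On recording, Section 8.3 says: "All adverse events, regardless of severity or the causal/effect relationship, will be recorded". On analysis, Section 9.4 says: "Summary tables will present incidence rates of adverse events by treatment group for all subjects who enter the treatment period".

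**The concern.** A causality scale should rise in step with the strength of the evidence. Here the wording that would normally describe a possible link, uncertain and with other causes open, sits under *Unlikely related*. *Possibly related* is worded almost as strongly as *Related* and adds a condition that *Related* lacks. An investigator who follows the text must call an undecided event unlikely.

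This matters because causality has one operational use in the plan, as the trigger for prompt notice to the study monitor. If *Unlikely related* is not treatment related, the events on which early notice would be most useful for forming a view are the ones held back. The investigator also knows which product each site received (Section 3.3), so unclear categories leave more room for judgement made with knowledge of treatment.

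**Working it through.** No arithmetic applies, and the plan gives no figure to reproduce. The check sets the definitions side by side and then traces example events through the reporting rules.

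**Step 1: the definitions compared.**

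| Category | Strength of association | Improvement on withdrawal | Other causes |
|---|---|---|---|
| *Not related* | none | not mentioned | event attributed to them |
| *Unlikely related* | uncertain | not mentioned | also possible |
| *Possibly related* | clear-cut | required | clinical state not a reasonable explanation |
| *Related* | clear-cut in time | not required | clinical state not a reasonable explanation |

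Two things follow. The scale goes straight from uncertain to clear-cut, so only *Unlikely related* can hold an uncertain association. On withdrawal, the weaker label *Possibly related* sets a stricter test than *Related*.

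**Step 2: can the withdrawal condition be observed?** Product is applied on one Treatment Day, and any remaining material is washed off only after the 6-hour sample (Section 5.1.3.3). Section 8.1 ends the capture of adverse events at discharge. Section 8.3 mentions a follow-up period without giving its length, and requires follow-up to resolution only for serious or unexpected events. For an expected, non-serious skin reaction, the plan therefore does not require the observation on which *Possibly related* depends.

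**Step 3: example events traced through the text.** The clinical state does not explain the event in any of these cases.

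| Event | Category that fits | Prompt notice to monitor |
|---|---|---|
| Non-serious, association uncertain, another cause possible | *Unlikely related* only | not triggered, if *Unlikely related* is not treatment related |
| Non-serious, clear-cut timing, improvement not observed | *Related* | triggered |
| Non-serious, clear-cut timing, improves after wash-off | *Possibly related* and *Related* both fit | triggered if coded *Related*; otherwise depends on the undefined term |
| Serious, association uncertain | *Unlikely related* only | sponsor informed within 24 hours in any case |

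The first row is the defect. The third shows that the two upper categories overlap, with no rule for choosing between them.

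**Step 4: what does not depend on the category.** All events are recorded whatever their cause. Section 9.4 tabulates them by treatment group with no causality filter and specifies no table by relatedness. Irritation scores of 1 or more are reported for any site (Sections 8.2 and 9.4), and a score of 3 is an adverse event by definition (Appendix 17.8).

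**The case against.** The strongest reply is that little turns on the wording. Every event is recorded, listed and tabulated. The adverse event form is part of the case report form, which the monitor reviews (Section 11). Section 8.1 asks for the causal relationship to the study procedure as well as to the product. Serious events are reported without regard to cause. All of this stands, and it confines the point to causality coding and the timing of notice for non-serious events. It does not remove the point: recording and later review are not prompt reporting, and a causality code assigned under these definitions will still misdescribe an undecided event.

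A reader might infer more than the documents support, in three ways.

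- *That any local reaction to which sampling scrub, clipping or dressing adhesive may have contributed must be coded* Unlikely related. It need not be. *Possibly related* and *Related* exclude only what the subject's known clinical state explains, and study procedures are not clinical state. A reaction with clear-cut timing can still be coded *Related*.
- *That the definitions push all attribution downward.* They do not. *Related* has no withdrawal condition, so clear-cut reactions that fail *Possibly related* on that ground move up. Only events whose association is itself uncertain move down.
- *That safety events would be lost or the safety tables biased.* The recording and tabulation rules rule this out.

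It can also be said that the plan never excludes *Unlikely related* from treatment related. That is true, and the missing definition is part of the defect.

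**Conclusion.** The concern holds in a limited form. The causality labels do not match their definitions: an uncertain association can be coded only as *Unlikely related*, and *Possibly related* carries a condition that *Related* lacks and that this design can hardly test. Because treatment related is not mapped to the categories, a non-serious event of uncertain cause would, on the natural reading, not be promptly reported.

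The conclusion rests on two assumptions: that investigators apply the definitions as written, as the section requires, and that *Unlikely related* falls outside treatment related. The documents contain nothing from which to estimate how many events have an uncertain cause, so no rate is offered. Serious event reporting, the recording of adverse events, the planned safety tables and the efficacy analysis are unaffected.

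**What to change.** In Section 8.3, under Causal Relations:

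- *Unlikely related*: the association is improbable and another cause is more likely.
- *Possibly related*: the association is uncertain, the timing is plausible and other causes are also possible. Remove the condition on withdrawal.
- *Related*: leave unchanged.

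Under Recording and Reporting, state that treatment related means *Possibly related* or *Related*. Carry the same wording onto the adverse event form.

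The direct cost is a few lines of text and a revised form. The consequences are a slightly higher count of possibly related events and a few more prompt reports to the monitor. No analysis or sample size changes.
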